Sample Size. Our estimate of the number of caregivers that we plan to enroll is based on the average number of unique patients and the smoking prevalence of caregivers seen in a 12-month period in the PED at CCHMC. Based on enrollment in previous studies (which had average annual enrollment of 300-350 caregivers), and a 30 month chart review on the number of annual visits for patients with SHS-related complaints (at least 6,000), we are conservatively expecting to enroll 300 caregivers who smoke over 12 months, for a total of 750 caregivers in 30 months. To obtain the effective sample size for power analyses of outcomes, the sample size must be adjusted for potential attrition of approximately 20% at 6 months, although all efforts will be used to decrease this attrition rate, leaving a total of 600; 300 per group.

Estimate of effect sizes: Evaluation of outcomes. Based on the recommendations of Hughes et al.,^{85,86} we will use 2 criteria for abstinence: 6-month point prevalence and prolonged abstinence at 6-months. Based on a similar prior study, we expect that 6-month point prevalence in the HHC condition will be 6.3%.⁵⁴ For prolonged abstinence, we are basing our estimation on the 2.1% rate for the HHC and 7% rate for SBIRT. We are conservatively estimating a point prevalence cessation rate of 6.3% and prolonged abstinence rate of 2.1% in the HHC group.⁵⁴ We are basing our estimate of 6-month point prevalence of the SBIRT group on the odds ratio derived from meta-analyses assessing the effectiveness of NRT vs. a control, ranging from 1.4-4.6,⁵⁴ to give a cessation rate of 10-12% in the SBIRT group. However, since a clinical counselor/intake coordinator/research coordinator will be conducting the intervention, we expect high compliance in implementation. Thus, we are estimating a cessation rate of 12% in the SBIRT group. Similarly, for prolonged abstinence, we are assuming a rate of 7% in the SBIRT group.

Power (Table 2). Power analyses are based on estimates of differences in both 6-month point prevalence and 6-month prolonged abstinence between groups. With 300 subjects in each group, we would have 80% power to detect an increase of 6.4% in cessation rate. However, assuming a multiple imputation approach, we would be able to detect a 5.5% increase in cessation rate.

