For 6-month abstinence, we can detect an increase of 4.5% with 300 subjects per group and 4.2% with the multiple imputation assumption. These estimates are consistent with the predicted cessation rates shown above and published rates.^{54,93} For analyses based on regression techniques, using hierarchical linear modeling, sample sizes will be more than sufficient. The effect sizes of interest for these analyses are the correlation

Table 2: Estimated Power for varying sample size

N / group	Odds ratio 80% power- prevalence	Odds ratio 80% power- abstinence	Assumption
300	2.16	3.29	20% loss
375	2.00	3.05	Multiple Imputation

coefficients and squared, semi-partial correlations (squared=incremental R^2). To predict caregiver level variables (Primary Aim 1), with a sample size of 750 and 20% lost to follow-up, we will have >80% power to detect a correlation of 0.11 ($r^2=0.013$). For examination of smoking bans (Primary Aim 2), these samples sizes would allow us to detect a difference of 12% with 80% power with 300 per group assuming a rate of between 50% and 65% in the HHC group. Using multiple imputation and 375 per group, we could detect a difference of 11% with 80% power.

Analytic Plan

Data analyses will be conducted at CCHMC and at the University of Cincinnati. A DTA will be established with study investigators at the University of Cincinnati. Data will include demographics, smoking behavior, data from the parent assessments, clinical data, and EMR data. The data will be a limited data set stripped of identifiers. It will be shared on an encrypted file.

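### Several cessation power figures do not follow from their own inputs, and the predicted point-prevalence difference is smaller than the one the plan says it can detect at 300 per group

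*Combined protocol and SAP*

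**What the plan says.** All the figures are in the combined protocol and SAP, under Sample Size and Power Estimates (paragraphs Sample Size, Estimate of effect sizes, and Power with Table 2).

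- **Analysable number.** Attrition of 20% is taken off 750, "leaving a total of 600; 300 per group". A second scenario keeps 375 per group on the assumption of multiple imputation.
- **Assumed rates.** For the control group, "we expect that 6-month point prevalence in the HHC condition will be 6.3" per cent. For the intervention group, an odds-ratio range of 1.4-4.6 is said "to give a cessation rate of 10-12% in the SBIRT group", and then "we are estimating a cessation rate of 12% in the SBIRT group". Prolonged abstinence is put at 2.1% and 7%.
- **Detectable differences at 80% power.** Point prevalence: 6.4 points at 300 per group and 5.5 at 375 (Table 2 odds ratios 2.16 and 2.00). Prolonged abstinence: 4.5 points at 300 and "4.2% with the multiple imputation assumption" (Table 2 odds ratios 3.29 and 3.05). The text then calls these estimates consistent with the predicted rates.
- **Correlation.** "with a sample size of 750 and 20% lost to follow-up", "we will have >80% power to detect a correlation of 0.11", with r-squared printed as 0.013.
- **Smoking bans.** The plan claims it can "detect a difference of 12% with 80% power with 300 per group", and 11 points at 375 per group, for a control rate of 50% to 65%.

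These paragraphs give no alpha, sidedness or test.

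**The concern.** A reader who puts the stated inputs into standard formulas does not get the stated outputs back. Some pairs of numbers also disagree with each other whatever test is assumed.

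Point prevalence matters most. It is a primary outcome, and the predicted effect is smaller than the effect the plan says it can detect with the participants it expects to retain. The section therefore suggests about 80% power for a primary comparison that has less at the planned rates. A non-significant result on point prevalence would be harder to interpret if readers believed the stated power.

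**Working it through.** **Assumption.** Two-sided alpha of 0.05, because none is stated. One-sided results are given where they change the reading.

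**1. Correlation.** Input: n = 600 (750 less 20%). Fisher z: power = Φ(atanh(r)·√(n − 3) − 1.96), with √597 = 24.43.

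- r = 0.11: 0.11045 × 24.43 = 2.699, and Φ(0.739) = 77.0%. One-sided 0.05 gives 85.4%.
- 0.11² = 0.0121, not 0.013. √0.013 = 0.114.
- r = 0.114: 0.1145 × 24.43 = 2.798, and Φ(0.838) = 79.9% (80.1% by the noncentral t).

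The smallest r detectable with 80% power is 0.114, so the plan's calculation is recovered from its r-squared but not from its printed r.

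**2. Text against Table 2 (no alpha needed).** Odds at 2.1% are 0.02145; odds at 6.3% are 0.06724.

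| Outcome, n per group | Table 2 OR | Implied difference | Text |
|---|---|---|---|
| Point prevalence, 300 | 2.16 | 6.38 points | 6.4 |
| Point prevalence, 375 | 2.00 | 5.55 points | 5.5 |
| Prolonged abstinence, 300 | 3.29 | 4.49 points | 4.5 |
| Prolonged abstinence, 375 | 3.05 | 4.04 points | 4.2 |

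Three pairs agree to rounding and the fourth does not. A rise of 4.2 points from 2.1% reaches 6.3%, and 0.06724 / 0.02145 = OR 3.13.

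**3. Power at the stated differences.** Pooled formula: power = Φ{[d − 1.96·√(2p̄(1 − p̄)/n)] / √[p₁(1 − p₁)/n + p₂(1 − p₂)/n]}.

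- 6.3% vs 12.7%, 300 per group: (0.064 − 1.96 × 0.02394) / 0.02380 = 0.718, so 76.3%.
- 6.3% vs 11.8%, 375 per group: (0.055 − 1.96 × 0.02095) / 0.02086 = 0.668, so 74.8%.
- 2.1% vs 6.6%, 300 per group: 77.2% pooled, 80.0% by arcsine.
- 2.1% vs 6.3%, 375 per group: 81.9% pooled.

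For the two point-prevalence figures, arcsine gives only 77% and 76%, and no two-sided variant tried reached 78%.

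Solving the pooled formula for 80% power gives:

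| Outcome | 300 per group | 375 per group |
|---|---|---|
| Point prevalence | 6.7 points (OR 2.23) | 5.9 points (OR 2.07) |
| Prolonged abstinence | 4.7 points (OR 3.41) | 4.1 points (OR 3.06) |

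**4. Power at the predicted rates.**

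- Point prevalence: 12 − 6.3 = 5.7 points. At 300 per group, (0.057 − 1.96 × 0.02354) / 0.02343 = 0.464, so 67.9%. At 375 per group, 77.4%.
- Prolonged abstinence: 7 − 2.1 = 4.9 points. At 300 per group, 82.3%.

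**5. Odds-ratio range (no alpha needed).** On 6.3%, OR 1.4 gives odds of 0.0941, a rate of 8.6%. OR 4.6 gives odds of 0.3093, a rate of 23.6%. Rates of 10% and 12% correspond to ORs of 1.65 and 2.03.

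**6. Smoking bans.** At the least favourable control rate, 50%, 12 points at 300 per group has 84% power and 11 points at 375 has 86%. Both claims are met.

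**The case against.** Alpha is not stated and the hypotheses are directional, so a one-sided test cannot be ruled out. One-sided 0.05 lifts r = 0.11 to 85%. With a continuity correction it gives 81.5%, 80.4% and 80.6% for the first three cessation figures, close to the claim. But it gives 85.2% for 4.2 points at 375, and no variant tried reproduces all four. Even on an uncorrected one-sided test, 5.7 points at 300 per group has 78%. The objection therefore limits how firmly the power percentages can be stated. It does not touch the comparison of 5.7 with 6.4, the Table 2 mismatch or the r-squared.

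The correlation gap is mostly rounding of r, with a greater-than sign where about 80% would be right. A reader might infer a real shortfall in the regression analyses; the printed r-squared does not support that.

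A reader might also infer that every power figure is unsound. The ban figures are true and conservative across the stated range. The 4.5-point figure has 80.0% power by arcsine, a legitimate method. The 4.2-point figure is adequately powered, and its only fault is disagreement with Table 2.

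On the odds ratios, it is tempting to say that starting at 10% conceals a lower cited effect. The plan does not say that both ends of the range were applied to 6.3%, the implied ORs of 1.65-2.03 lie inside it, and 12% is far below its upper end. What stands is that the OR actually used is not given.

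Finally, the consistency statement directly follows the prolonged-abstinence figures, for which it holds (4.9 against 4.5 points). On the plan's own numbers it also holds for point prevalence at 375 per group (5.7 against 5.5). It fails for point prevalence at 300.

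**Conclusion.** The concern holds for the cessation figures and the printed correlation. Three findings need no assumption about the test: r and r-squared disagree; 4.2 points and OR 3.05 disagree; and the predicted 5.7 points is below the plan's own detectable 6.4 at 300 per group. The stated odds-ratio range also does not yield 10-12% when applied to 6.3%.

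Under a two-sided 5% test, the stated point-prevalence differences fall about 4 to 5 power points short of 80%. Power at the predicted rates is about 68% at 300 per group. The 77% at 375 takes multiple imputation to restore the full sample, which is the plan's assumption and was not tested here.

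A reader might go further and conclude that enrolment must rise. The documents do not support that as a correction: 750 is derived from expected accrual of 300 caregivers a year over 30 months, and prolonged abstinence, the other primary outcome, has 82% power at its predicted rates with 300 per group.

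**What to change.** In the power section:

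- State alpha, sidedness and one formula, and use them throughout.
- Print r = 0.114 with about 80% power, or keep r = 0.11 with 77%, and make r-squared agree.
- Restate the cessation text and Table 2 together. On the pooled two-sided 5% formula, the entries are the differences and odds ratios in the second table of the working.
- Give the power at the predicted 5.7 points (68% at 300 per group, 77% at 375 on that formula), and limit the consistency statement to the comparisons for which it holds.
- State which odds ratio led to 10-12% and why it was chosen from the range.

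Leave the smoking-ban figures as they are. The cost is a recalculation and a text edit, with no change to enrolment, procedures or analyses.

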Preliminary Analyses. Univariate and bivariate examination of variables will be done first. Distributional properties of the continuous outcome variables will be examined. To control for non-normal distributions and heterogeneous error variances, we will use logarithmic transformation and report geometric means and associated 95% confidence intervals; this is particularly relevant for cotinine. We will conduct several preliminary analyses prior to addressing the Study Aims: (1) Examination for out of range values; (2) Comparison of baseline characteristics of caregivers and children across groups. If baseline differences are found, further analyses will include these variables as covariates in assessing caregiver and child outcomes as appropriate; and (3) Attrition analyses to assess if: Participants who were lost to follow-up are different from those retained. Although we do not expect differential attrition by group, it will be evaluated and if it occurs, we will weight the follow-up data to reflect the proportion assigned to each group. If key variables significantly predict attrition, we will examine the analysis with and without the drop-outs. Thus, we will compare our primary outcomes using a multiple imputation approach for missing data to allow maximum utilization of our data. When including those that were lost to follow-up, the outcome data may be weighted using a response propensity analysis^{94,95} which uses the baseline distributions on these variables so that follow-up data has the same distributions on these variables as the baseline data. For all analyses we shall include in the model an indicator variable to account for which clinical counselor/intake coordinator/research coordinator was involved in the delivery of the SBIRT or HHC.

General approach for addressing study aims. This is a two-group RCT, wherein caregivers are randomly assigned to the SBIRT Group vs. HHC group. The appropriate statistical models for analyses of data for inclusion of time dependent outcomes are General Linear Mixed Models (GLMM) for data either with a Gaussian/normal distribution or with a binomial or Poisson distribution, using the appropriate link function, invoking Generalized Estimating Equations (GEE) to account for the longitudinal aspect of the data.⁹⁶

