We will use GLMM to evaluate the relative effectiveness of the SBIRT versus HHC group on our primary outcomes: point prevalence and prolonged abstinence at 6-months. The analysis will be repeated with caregiver level differences between groups included as covariates. We will use mixed model analysis of covariance, with repeated measures to assess change (controlling for baseline differences between groups) to assess the effect of the SBIRT on secondary outcomes including reduction in use, number of quit attempts, and changes in readiness to quit. Kappa statistic will be used to assess agreement between the caregiver's self-report and the assessment of tobacco use based on expired carbon monoxide levels and/or salivary cotinine at 6 months. It is possible that use of and adherence to the NRT will influence outcomes in the intervention group. In addition, some of the participants in the control condition may obtain NRT during the study interval. We will examine NRT use or dose, defined as self-reported adherence, as a covariate in order to control for this possible relationship.

Analyses for Primary Aims 1-3.

Primary Aim 1, Hypothesis 1: We hypothesize that SBIRT participants will have higher prolonged abstinence and point prevalence cessation rates compared to those in the HHC group. As stated above, our primary approach to the analysis is using multiple imputation, with clinical counselors/intake coordinators/research coordinators included in the model. We shall then use analysis of covariance, to control for any baseline differences of caregivers between conditions. In addition we will also control for motivation to quit, considered a priori as a potential covariate, using the score on the contemplation ladder. As we are stratifying on motivation to quit and caregiver gender, we will initially enter this into the model as an interaction. To address child cotinine as the 6-month outcome, we will use a t-test and then an analysis of covariance to incorporate the variables different at baseline. Incorporating the 6-week outcome values, we will use GLMM invoking GEE for the repeated

measures and also a model including covariates. This approach will be used to assess the intervention's effect on abstinence and point prevalence and child cotinine.

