Primary Aim 2, Hypothesis 2: We will evaluate the effectiveness of the SBIRT on total home/car smoking bans and on child SHSe which will be measured by both caregiver report and child salivary cotinine, as recommended by Halterman et al.⁸⁷ The reliability of caregiver's reports will be examined by comparing amount of smoking and SHSe levels reported at 6-months using Pearson's correlations. For validation, we will compare the child's salivary cotinine concentrations for those reporting total home/car smoking bans and those not, we shall also examine the change in cotinine levels from baseline for those initiating bans versus not. The computational procedure will use data from the 2 measurement points, controlling for the within-subject correlation of measures repeated over time.^{97,98} The main analysis will use GLMM, first to assess the intervention effect alone and then including covariates. First, we will investigate immediate intervention effects based on change from baseline to 6-weeks post-intervention. Next, we will investigate change from 6-weeks to 6-months to examine maintenance effects. To examine overall change, we will use GEE, examining linear and quadratic terms for time, group, and group \times time interactions as explanatory variables.⁵² Use of NRT, described above, may be of particular interest as a covariate for this analysis.

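### Beyond motivation, strata and interventionist, covariates are chosen by observed baseline imbalance, so baseline child cotinine is not a fixed covariate in the 6-month cotinine analysis

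*Combined protocol and SAP*

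**What the plan says.** Under Preliminary Analyses (Analytic Plan), the groups are first compared at baseline, and then: "If baseline differences are found, further analyses will include these variables as covariates", for caregiver and child outcomes alike, where judged appropriate. No test, threshold or list of candidate variables is given. The General approach section has the primary-outcome model repeated with the caregiver differences between groups as covariates. For child cotinine at 6 months, the Primary Aim 1 paragraph states: "we will use a t-test and then an analysis of covariance to incorporate the variables different at baseline".

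Three covariates do not depend on imbalance:

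- Motivation (Primary Aim 1): "In addition we will also control for motivation to quit, considered a priori as a potential covariate, using the score on the contemplation ladder".
- Stratification factors (Primary Aim 1): "As we are stratifying on motivation to quit and caregiver gender, we will initially enter this into the model as an interaction".
- Interventionist (Preliminary Analyses): "For all analyses we shall include in the model an indicator variable", identifying who delivered the session.

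The Primary Aim 2 paragraph, which also covers child salivary cotinine, uses baseline in a different way: "we will investigate immediate intervention effects based on change from baseline to 6-weeks post-intervention". It then takes change from 6 weeks to 6 months, and a GEE model with linear and quadratic time, group, and group by time terms.

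The Biochemical Validation section plans saliva from each child at baseline and 6 weeks, and only possibly at 6 months.

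**The concern.** In a randomised trial a baseline difference between arms arises by chance. Finding one does not show that the variable predicts outcome, and prediction of outcome is what makes adjustment worthwhile. A rule triggered by imbalance therefore has two costs. The adjusted model cannot be written down before the data are seen. And a strongly prognostic variable is usually left out, because chance rarely produces a detectable difference in it.

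Baseline cotinine is the clearest case. It is the same measurement as the outcome, taken earlier in the same child, and it is planned for everyone. What is at stake is precision in the child cotinine analysis and a pre-specified model, not the validity of the randomised comparison.

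**Working it through.** **Inputs from the plan.** The trigger rule, the t-test followed by ANCOVA, the 6-week change score, and 300 per group after 20% attrition (Sample Size). The plan gives no power figure for child cotinine, so there is none to reproduce. Its power statements concern abstinence, smoking bans and correlations, and they do not enter this check.

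**Assumed inputs.** Two-sided alpha of 0.05; a trigger of p<0.05; correlation r between baseline and follow-up log cotinine of 0.3 to 0.8; differences in SD units. The plan states none of these. The 300 per group is a convenient yardstick, not the expected 6-month saliva sample.

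**Step 1: how often the trigger fires.** Under randomisation a given variable reaches p<0.05 in 5% of trials (4.6% to 5.1% in simulation), so it is left out in about 95%. If k independent variables are examined, the chance that at least one is added is 1 − 0.95^k: 23% for k = 5 and 40% for k = 10. The content of the adjusted model is then largely a matter of chance.

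**Step 2: reference difference.** The difference with 80% power by t-test at 300 per group is (1.960 + 0.842) × √(2/300) = 0.229 SD.

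**Step 3: compare the analyses at that difference.** Relative to a follow-up variance of 1, ANCOVA on baseline has variance 1 − r² and a change score has variance 2(1 − r), taking equal SDs at both times. Power = Φ(0.229 × √150 / √variance − 1.96). For r = 0.5 with ANCOVA: 2.80/√0.75 = 3.24, and Φ(1.28) = 89.9%.

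| r | 1 − r² | t-test | ANCOVA always | Change score | n per arm for 80%, ANCOVA |
|---|---|---|---|---|---|
| 0.3 | 0.91 | 80% | 83.6% | 65.8% | 273 |
| 0.5 | 0.75 | 80% | 89.9% | 80.0% | 225 |
| 0.7 | 0.51 | 80% | 97.5% | 95.1% | 153 |
| 0.8 | 0.36 | 80% | 99.7% | 99.3% | 108 |

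The last column is 300 × (1 − r²). The factor 1 − r² holds whatever the sample size.

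**Step 4: the conditional rule itself.** Simulating ANCOVA used only when baseline cotinine differs at p<0.05 (10,000 trials per setting) gives power of 81.5%, 81.6% and 81.9% at r = 0.5, 0.7 and 0.8. Almost none of the available gain is recovered. Type I error is 4.2%, 4.0% and 3.3%, so the rule is conservative.

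**Step 5: a second difference.** At 0.2 SD and 300 per group (4,000 simulated trials), the t-test, the conditional rule and fixed ANCOVA give 68.7%, 69.7% and 81.3% at r = 0.5, and 69.5%, 71.3% and 92.6% at r = 0.7. The pattern is the same.

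**Abstinence.** No equivalent calculation is possible. Every caregiver is a daily smoker at entry, so the outcome has no baseline value, and the documents give no figure for how strongly any covariate predicts quitting.

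**The case against.** The plan is better than the trigger sentence alone suggests, and several stronger readings fail.

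- A reader might infer that covariates enter only through imbalance. They do not: the contemplation ladder, the stratification factors and the interventionist indicator are written in regardless. The wording is soft (motivation is called a potential covariate, and the strata are entered initially), and a plain t-test contains none of them.
- A reader might infer that baseline cotinine is never used. Primary Aim 2 takes change from baseline to 6 weeks, and its quadratic time term needs three time points, which implies that baseline is in that model. At r = 0.7 the change score is only about 2 points behind ANCOVA. This stands, but it does not repair the 6-month t-test, and at r = 0.3 or 0.5 the change score loses 10 to 18 points.
- A reader might infer a power loss on the primary abstinence outcomes. None is shown, and the main prognostic covariate that the plan names for them is already in the model.
- A reader might take 300 per arm as the 6-month cotinine sample. The Assessments section ties the 6-month home visit to reported abstinence and bans, so the real sample would be smaller and selected. Adjustment for baseline does not cure that selection.
- A reader might fear inflated false positives. For the cotinine rule examined here the simulated type I error is below 5%. For the primary outcomes the covariate model repeats the main one and does not replace it.

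**Conclusion.** The point holds in a limited form. Outside three pre-specified items, covariate choice depends on observed imbalance, and the 6-month child cotinine analysis has no fixed adjustment for baseline cotinine. The omission rate of about 95% depends on an assumed p<0.05 trigger; the plan leaves the criterion open. The gain from fixed adjustment is about 4, 10 and 17 points over a t-test with 80% power at r = 0.3, 0.5 and 0.7. Over the 6-week change score it is about 18, 10 and 2 points. The correlations, the SD scale and the sample size are assumptions, so these are illustrations; the variance factor 1 − r² does not depend on n. This is a matter of efficiency and pre-specification that should be corrected before analysis. It does not threaten the validity of the trial, and no loss is claimed for abstinence.

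**What to change.** Delete the baseline-difference trigger from Preliminary Analyses and from the Primary Aim 1 paragraph, and keep the baseline table as description.

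For child cotinine, specify ANCOVA on log cotinine with baseline log cotinine in every model, at 6 weeks and at 6 months. This replaces the 6-month t-test and the 6-week change score. Because undetectable values are to be recorded as 0 ng/ml, state how they are handled before taking logs; the planned log transformation needs that rule in any case.

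For abstinence, make the contemplation ladder, readiness stage and caregiver gender fixed covariates, and name any addition in advance. Baseline nicotine dependence is one candidate: Table 1 lists it at baseline, and the plan already treats it as a moderator.

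All these variables are already collected, so the cost is SAP wording only.

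### The planned weighting for differential attrition cannot change either arm's quit rate, and no sensitivity analysis covers loss that depends on unobserved smoking at follow-up

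*Combined protocol and SAP*

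**What the plan says.** The combined protocol and SAP treats attrition in the Preliminary Analyses paragraph of the Analytic Plan. Loss that differs by arm is introduced with "Although we do not expect differential attrition by group, it will be evaluated and if it occurs"; the response that the plan then commits to is "we will weight the follow-up data to reflect the proportion assigned to each group". On loss predicted by participant characteristics: "If key variables significantly predict attrition, we will examine the analysis with and without the drop-outs". The paragraph then adds that "we will compare our primary outcomes using a multiple imputation approach for missing data", and that, with those lost brought in, "the outcome data may be weighted using a response propensity analysis". The plan describes this method as one "which uses the baseline distributions on these variables so that follow-up data has the same distributions on these variables as the baseline data".

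Under Primary Aim 1, Hypothesis 1, the plan states that "our primary approach to the analysis is using multiple imputation". It names motivation to quit as an a priori covariate. A further, longitudinal model is given in the sentence that begins "Incorporating the 6-week outcome values, we will use GLMM invoking GEE for the repeated". The variables in the imputation model are not listed. No section sets a missing = smoking rule, a delta-adjusted or pattern-mixture imputation, or a tipping-point analysis.

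**The concern.** The arm-proportion weighting is the only firm commitment tied specifically to differential attrition. Its weight is the same for every retained caregiver in an arm. Bias from attrition arises because those retained in an arm differ from those lost from it, and a constant cannot rebalance people within an arm. The weighting that could do so, on response propensity, is only optional. It has no stated trigger, is not said to be fitted by arm, and balances baseline variables only.

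The second gap concerns the missing-at-random assumption. A caregiver who relapses after the last contact and then stops answering is lost for a reason that the recorded data need not explain. The plan expects 20% loss and low quit rates. At the planned rates, 600 retained caregivers yield about 300 × 0.12 + 300 × 0.063 = 54.9 quitters, while 150 caregivers are missing. What is assumed about those 150 can therefore matter to the comparison.

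**Working it through.** **Inputs.** From Sample Size and Power Estimates: 750 randomised, about 20% attrition, 6-month point prevalence 12% (SBIRT) v 6.3% (HHC). Equal allocation, 375 per arm, is implied by the plan's 300 per group. Alpha is not stated for the power figures; two-sided 0.05 is assumed. All arm-specific retention splits below are assumptions, because the plan gives only 80% overall.

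**The plan's own figure.** 750 × (1 − 0.20) = 600, or 300 per group. This reproduces.

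**Effect of the arm-proportion weight.** Weight in an arm = assigned share / retained share = w, constant within the arm. Weighted rate = (w × quitters) / (w × retained) = quitters / retained.

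- Retained 330 SBIRT and 270 HHC, with 40 and 17 quitters. Weights are 0.5/(330/600) = 0.909 and 0.5/(270/600) = 1.111. Rates are 12.12% and 6.30% before and after. The odds ratio (OR) is (40/290)/(17/253) = 2.053 before and after. Only the pooled rate (9.50% to 9.21%) and the model standard error of the log OR (0.302 to 0.296) move.
- Retained 270 SBIRT and 330 HHC, with 32 and 21 quitters. Rates are 11.85% and 6.36%, and the OR is (32/238)/(21/309) = 1.978, again unchanged.

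**What outcome-related loss can do (illustration).** Suppose the true rate is 9% in both arms. SBIRT retains 95% of abstainers and 75% of smokers; HHC retains 80% of both. The observed SBIRT rate is 0.0855/(0.0855 + 0.6825) = 11.1%, against 9.0% in HHC. The OR is 1.27 with no true effect, and the arm-proportion weight leaves it at 1.27.

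**Missing = smoking.** Rate = rate in those followed × retention. In those followed, the OR is (0.12/0.88)/(0.063/0.937) = 2.03 and the difference is 5.7 points.

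| Retention SBIRT/HHC | SBIRT | HHC | Difference (points) | OR | Power, 375 per arm |
|---|---|---|---|---|---|
| 80%/80% | 9.6% | 5.0% | 4.6 | 2.00 | 67% |
| 72%/88% | 8.6% | 5.5% | 3.1 | 1.61 | 38% |
| 88%/72% | 10.6% | 4.5% | 6.0 | 2.48 | 88% |

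The last OR is (0.1056/0.8944)/(0.04536/0.95464) = 2.48.

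Power uses the pooled two-proportion formula: z = [|p1 − p2|√n − 1.96√(2p̄(1 − p̄))] / √(p1(1 − p1) + p2(1 − p2)). For 12% v 6.3% followed at 300 per arm it gives 68%, which is the comparator for the 67%.

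**Grid of departures.** Take 20% loss in each arm. Set the odds of abstinence in the lost, relative to those followed, anywhere from 0 to 1 separately by arm. The OR then runs from 1.58 (all missing SBIRT caregivers smoke; missing HHC caregivers resemble those followed) to 2.57 (the reverse). The difference runs from 3.3 to 7.0 points.

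**The case against.** The strongest reply is that the weighting sentence is a contingent preliminary step. The primary approach is multiple imputation, and once outcomes are imputed for everyone randomised, the assigned proportions are restored and the weight has nothing to do. Tobacco use, dependence and motivation are collected at baseline, motivation is an a priori covariate, and 6-week outcomes enter a repeated-measures model. All of this stands.

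It rules out two stronger readings that a reader might infer. One is that no planned analysis deals with smoking-related loss at all. The documents do not support this, because the named methods can address loss explained by observed smoking variables if those variables are included. The other is that the trial would report a supposedly corrected result carrying the whole bias. Nothing says that the weighted result replaces the imputed one, and nothing shows that imputation would remove none of the bias. In a covariate-adjusted model the weights may also shift the estimate slightly.

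It is also fair to say that missing = smoking at equal retention is nearly harmless. The risk ratio stays at 1.90 (0.12/0.063 = 0.096/0.0504), and the smaller difference is a rescaling of both arms. Unequal retention can raise or lower the OR, so one unfavourable split alone would mislead. Missing = smoking is itself a strong assumption: in the no-effect illustration above it gives 8.55% v 7.2%, an OR of 1.21 and not 1.

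The reply does not rescue the weighting, which does nothing for the unadjusted contrast. Nor does it fill the second gap. The comparison with and without drop-outs is conditional, and it brings drop-outs in through imputation or weights built on observed data.

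**Conclusion.** The concern holds in two limited parts. First, the stated response to differential attrition leaves both arm rates and the unadjusted contrast exactly as they were. This is algebra and needs no assumption about the data. Second, every named method relies on observed data under missing at random, and none examines loss that depends on unobserved smoking status at follow-up.

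The size of the second part rests on assumed retention splits and on taking the planned rates as those in caregivers followed. Under missing = smoking, the OR of 2.03 becomes 2.00 with equal 80% retention, 1.61 with 72%/88% and 2.48 with 88%/72%. The exposure therefore lies in unequal or outcome-related loss. Equal loss costs almost no power. The plan does not expect unequal loss, so this is a safeguard to repair and does not show that the primary analysis is biased.

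**What to change.** Delete the arm-proportion weighting. If attrition differs by arm, weight those followed by the inverse of the response probability, estimated within each arm from baseline variables (smoking, dependence, motivation). Keep multiple imputation as primary and list the variables in its model. Pre-specify two sensitivity analyses for the abstinence outcomes: (a) missing = smoking, and (b) delta-adjusted imputation over a grid of quit odds for missing caregivers, varied separately in both arms and not in SBIRT only.

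No new data are needed. The cost is SAP wording, a little extra programming, and slightly wider intervals under the response weights.
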